5.3 Study Treatment Administration

5.3.1 Study Treatment Periods

5.3.1.1 Single-Blind Run-In Placebo Administration

During the placebo run-in period subjects will be instructed to administer study medication (Cohort A: 1 capsule from each bottle; Cohort B: 1 capsule) at night prior to bedtime (@ $10 \text{ PM} \pm 90$ minutes each night no sooner than 2 hours after dinner). Subjects will be dispensed sufficient placebo to continue self-administration until they return for Visit 2. At Visit 2, unused placebo will be collected and compliance will be reviewed. Subjects will be re-dispensed the placebo to continue self-administration until they return for Visit 3, including instructions to continue daily administration at home at bedtime (@ $10 \text{ PM} \pm 90 \text{ minutes}$ each night no sooner than 2 hours after dinner).

5.3.1.2 Double-Blind Treatment Administration

In Part 1 all subjects will receive double-blind placebo or ORMD-0801 according to their randomization schedule.

Subjects in Cohort A only will undergo a step-wise dose escalation during the first two weeks to reach the target dose. ORMD-0801 dosing will begin with 16 mg administered QHS, BID or TID for the first week then increase to 24 mg for the second week. Dosing at 32 mg will commence at the beginning of Visit 5 (Start of Part 2) and continue through until Visit 9.

Subjects in Cohort B will remain on their randomized dosing regimen throughout Part 1 and Part 2.

5.4 Dose Modifications

Dose modifications will be discouraged, however modifications in dose level are permitted to avoid hypoglycemia if necessary in Cohort A only. The IWR system will be used to modify allocation of study medication as required to accommodate any blinded dose adjustments. This may also apply to subjects who are rescued during Part 2 (for persistent hyperglycemia) as they will receive additional approved glucose lowering agents while continuing their blinded study medication regimen.

If any subject on active treatment or placebo experiences worsening hyperglycemia, they may be eligible for rescue (Section 3.7). Subjects requiring additional treatment not otherwise eligible for rescue will be considered for discontinuation and referral (Section 4.3).

5.5 Measuring Subject Compliance

Dosing compliance will be assessed through review of diary entries as well as a count of unused study medication at each clinic visit.

5.6 Drug Accountability

In accordance with current GCP, the Investigational Site will account for all study treatment supplies. Details of receipt, storage, administration, and return or destruction will be recorded in the Investigational Drug accountability record according to the SOP of the Investigational Site. Copies of the Investigational Drug accountability record will be provided to the Sponsor. Study treatment will only be dispensed to subjects enrolled in this protocol, and only as directed by this protocol. Administration of study treatment will be accurately recorded in each subject's source documents and in the eCRF.

5.7 Concomitant Medications and Supplements

All medications and supplements (other than study treatment) taken by the subject from Visit 1 through the Follow-up Visit 10 will be considered "concomitant" medications and supplements. Medications and supplements taken prior to Visit 1 that are no longer being taken at the time of Visit 1 will be considered "prior" medications and supplements.

All medications and supplements taken within 30 days prior to the first dose of study treatment and concomitant medications and supplements taken during the course of the study will be recorded in the subject's source documentation and in the eCRF.

If a subject requires the use of any of the prohibited medications and supplements listed below, the investigator will contact the Sponsor and the Medical Monitor to discuss the subject's continued participation in the study. In the event of an emergency, subjects will be treated at the discretion of the investigator according to acceptable community standards of medical care. The following are prohibited medications:

- 1. Any Investigational Drug other than ORMD-0801 (or placebo) within 30 days prior to Visit 1 through the Follow-Up Visit 10;
- 2. Any anti-diabetic drugs (except for those allowable by the inclusion criteria) including insulin, GLP-1 analogue, α-glucosidase inhibitors, glinides, and pramlintide unless required for rescue;

- 3. Thyroid preparations or thyroxine (except in subjects on stable replacement therapy);
- 4. Systemic long-acting corticosteroids or other systemic corticosteroids or inhaled corticosteroids (if daily dosage is > 1,000 μg equivalent beclomethasone). Intra-articular and/or topical corticosteroids are not considered systemic.
- 5. Medications known to modify glucose metabolism or to decrease the ability to recover from hypoglycemia such as oral, parenteral, and inhaled steroids, and immunosuppressive or immunomodulating agents.

If the subject initiates prohibited drug therapy, or if the investigator determines that use of a prohibited therapy is in the best interest of the subject's health and well-being, the investigator and sponsor will jointly decide to continue or discontinue study treatment for the subject.

Medications and supplements should be recorded according to the generic name when possible. The use of concomitant medications and supplements should be limited to those that are medically necessary. Any medication or supplement used should have an indication recorded, and for concomitant medications and supplements, this indication must be represented as either for the treatment of an AE, for the management of a pre-existing condition, or for prophylaxis.

Dosage increases for any concomitant medication or supplement should be noted and the reason for the dosage increase recorded as an AE (assumes worsening condition). The side effects of concomitant medications will be recorded as AEs.

Any subject whose condition becomes disqualifying during the course of the study may be treated for that condition. If the condition is suspected during Screening, the subject should not be enrolled. Treatment of the condition should be instituted according to the Investigator's/attending physician's judgment.

Medications that have no treatment intent but rather are part of supportive routine care such as local anesthetics, intravenous solutions to maintain fluid balance and keep access open, medications used for prophylaxis, and narcotics for postsurgical pain must also be recorded in the subject's medical record and eCRF

5.8 Dietary Restrictions

Subjects will fast overnight for at least 8 hours (10 hours recommended) prior to Screening and prior to all subsequent study visits.

Excessive caffeine use (i.e., more than five cups of caffeinated beverages per day) will not be allowed from Screening through the Follow-Up Visit 10. Excessive alcohol use or binge drinking will be discouraged during the study, and alcohol will be prohibited 72 hours prior to each visit).

Subjects will also be asked to refrain from any unusual or unaccustomed vigorous exercise during the course of the study.

6 STUDY PROCEDURES AND ASSESSMENTS

6.1 Safety Assessments

6.1.1 Weight and Height

Weight will be measured at visits indicated in Table 1. The subject will be clothed while being weighed, but should remove shoes, coats, jewelry and other accessories. Height will be measured at Screening only with the subject wearing no shoes.

6.1.2 Vital Signs

Vital signs (including seated SBP/DBP, and heart rate) will be recorded at all visits as described in Table 1. Vital signs will be measured after the subject has been sitting for at least 5 minutes in a quiet environment and prior to any blood draw that occurs at the same time point. The recorded seated SBP/DBP value will be the mean of two measurements taken 2 minutes apart and always using the non-dominant arm.

6.1.3 Physical Examination

A physical examination will be performed as described in Table 1, or in case of Rescue Visit or Early Withdrawal. The physical examination will include the following organ or body system assessments: skin; head, eyes, ears, nose, and throat; thyroid; lungs; cardiovascular; abdomen (liver, spleen); lymph nodes; and extremities, as well as an abbreviated neurological examination. During the Follow-up Visit 10, an abbreviated physical exam will be performed to note any newly developed abnormalities.

6.1.4 12-Lead ECG

A 12-lead ECG will be performed at Screening and at Visit 9 or in case of a Rescue Visit or Early Withrdawal . The 12-lead ECG will be recorded after the subject has been resting at least 5 minutes in the supine position in a quiet environment. ECGs will be read for QT and QTc (Federicia's) intervals and clinically significant abnormalities. At the Investigator's discretion, an additional ECG may be performed at the end of treatment; however, it will be recorded in source documents as an unscheduled assessment.

6.1.5 Clinical Laboratory Tests

Blood and urine for clinical safety laboratory assessments will be collected and processed using standard procedures at indicated in Table 1. A central laboratory will perform all clinical laboratory tests.

In the event of abnormal clinical laboratory values, the Investigator will make a judgment whether or not the abnormality is clinically significant.

6.1.5.1 Clinical Safety Labs

The clinical safety labs will include the following hematology, serum chemistry, and urinalysis tests:

Protocol No. ORA-D-015 Page 44

Hematology

- Hematocrit
- Hemoglobin
- Mean corpuscular hemoglobin
- Mean corpuscular hemoglobin concentration
- Mean corpuscular volume
- Platelet count
- Red blood cell distribution width
- Red blood cell count
- White blood cell count with differential

Serum Chemistry

- Sodium
- Potassium
- Chloride
- Bicarbonate
- ALT
- AST
- Gamma-glutamyltransferase (GGT)
- Total bilirubin
- Alkaline phosphatase
- Albumin
- Total Protein
- Blood urea nitrogen (BUN)
- Creatinine
- Uric acid
- Glucose
- Calcium
- Phosphorus
- Total cholesterol
- Triglycerides

Urinalysis

- Appearance (color and character)
- Bilirubin
- Urobilinogen
- Protein
- Glucose
- Ketones
- Leukocyte esterase
- Urine blood
- Nitrite
- pH
- Specific gravity

6.1.5.2 Pregnancy Test

A serum pregnancy test will be performed for WCBP at Screening. A urine pregnancy test will be performed for WCBP at Visits 1-10 and during Rescue Visits.

6.1.5.3 Immunogenicity Testing

Samples will be drawn to test for antibodies to insulin pre-dose at Screening, then at Visit 9 and in case of Early Withdrawal.

6.1.5.4 Additional Screening Bloodwork

In addition to the blood tests listed above, A1C, FPG, C-peptide, and TSH will be measured according to Table 1.

6.1.5.1 Drugs of Abuse

Drugs of abuse urine screens will be completed as indicated in Table 1, according to the laboratory manual provided by the central laboratory. These will include testing for amphetamines, barbiturates, cocaine metabolites, opiates, and benzodiazepines.

6.2 Efficacy Assessments

6.2.1 Mixed Meal Tolerance Test (MMTT)

All subjects will have mixed meal tolerance testing throughout the study. MMTT will be performed as indicated in Table 1. All subjects will report to the research center following a 10 hour fast prior to taking morning medications. All MMTT should be scheduled at the same time for each subject. If the fasting blood glucose value measured on the day of the Rescue Visit remains > 250 mg/dL, then no MMTT test will be performed but an attempt will be made to reschedule.

- 1) Baseline blood samples will be drawn at -50 minutes (±10 minutes) and at -5 minutes (±5 minutes) from the start of the meal. Blood samples will be drawn for insulin, glucose, and C-peptide levels.
- 2) 45 minutes prior to the start of the meal (time 0), subjects will receive their morning dose of study drug (active or placebo, depending on the Visit). Subjects' blood glucose (BG) must be >70 mg/dL and <250 mg/dL prior to initiating dosing.
- 3) At 0 time, the subject will receive a standardized meal, which should be ingested over 5 minutes.
- 4) Additional blood samples will be drawn at 60 and 120 minutes (\pm 10 minutes) after the start of the meal to obtain insulin and glucose levels. Samples for C-peptide will also be drawn at 60 minutes (\pm 10 minutes).

6.2.2 Self-Monitored Blood Glucose (SMBG)

Subjects will be asked to collect daily blood glucose measurements throughout the study using the supplied glucose meter. SMBG profiles must be obtained during any 1-2 days within 5 days of the next study visit. This means subjects could perform SMBG on 1-2 consecutive days (e.g. just prior

to their study visit) or on 1-2 non-consecutive days if they are completed within the 5 days immediately preceding a study visit.

SMBG profiles must be collected at specific times relative to outpatient dosing and meals. It is important for subjects to take the post-prandial fingerstick glucose measurement within this time.

It is important to remind subjects to record the times of dosing, the times of meals and the times of fingerstick blood glucose measures particularly during the dose escalation period.

• 7-Point Self-Monitored Blood Glucose Profiles

7-Point SMBG profiles should include self-glucose measurements in the morning (while fasting and just prior to taking study medication) and ~ 60 minutes (1 hour) after eating breakfast; again both prior to and 60 minutes after lunch and dinner. A final measurement should be taken prior to bedtime.

6.2.3 Continuous Glucose Monitoring

CGM Dexcom G4 devices will be provided at Visit 1 and Visit 8. Data will be collected for 2 weeks. Subjects will be taught how and when to calibrate the device during the collection period. Subjects must be instructed that NO ACETAMINOPHEN usage should occur during the CGM monitoring periods. Investigator should inquire and subjects should notify the study staff if they used acetaminophen (or any acetaminophen containing products) during the CGM monitoring period.

6.3 E-Diary

At Run-in Visit 1, eligible subjects will be given an e-diary and will be trained to enter specific data into the diary.

The diary will include sections for:

- SMBG values and time of day, subjects.
- Dosing time(s) for study drug (active or placebo) administration
- Time of day and type of meal (breakfast, lunch, dinner, and snacks)
- Information related to hypoglycemia: exact time and date of hypoglycemia; symptoms, if any; treatments, if any; and specific circumstances.
 - Subjects should record how the episode was resolved using the text input on the E-Diary and specifically record
 - Did they require assistance from someone else to resolve the hypoglycemia
 - This means that without the help of another person the subject would probably not have been able to help themselves including being able to obtain and self-administer glucose.
 - This would include the requirement for medical assistance or administration of glucagon

 Did they experience confusion, or changes in their ability to think and act (such as becoming irritable or aggressive and not understanding their condition?)

The Principal Investigator or designee will review diary data at clinic visits and will provide advice on glucose control if necessary.

7 ADVERSE EVENTS AND SAFETY REPORTING

7.1 Safety and Tolerability Assessments

Safety and tolerability will be assessed on an ongoing basis by review of reported AEs, physical examinations, 12-lead ECGs, weight, vital signs (SBP/DBP and heart rate), and clinical safety labs (hematology, serum chemistry, and urinalysis).

7.2 Definition of Adverse Event

An adverse event (AE) is defined in 21 CFR 312.32(a) as follows:

Any untoward medical occurrence associated with the use of a drug in humans, whether or not considered drug related.

An AE can be any unfavorable and unintended sign (e.g., an abnormal laboratory finding), symptom, or disease during the course of the study, and does not imply any judgment about causality.

Treatment-emergent adverse events (TEAEs) are defined as any AE that starts or increases in severity after the first randomized dose of study treatment (active or placebo).

7.3 Adverse Events of Special Interest

7.3.1 Adverse Events of Hypoglycemia

Episodes consistent with hypoglycemia will be reported as adverse events of special interest. Due to the specific relevance of hypoglycemia as a limiting factor in insulin therapy, AEs of hypoglycemia will be reviewed at every visit. All hypoglycemic events, including those that occur during clinic visits and those that are recorded in e-diaries, will be reported on a special hypoglycemia AE eCRF page. This will include the following information:

- Subject symptoms
- Type of symptoms
- BG value during the hypoglycemic event and the event severity based on CTCAE criteria
- whether treatment was required
- whether assistance was required for treatment
- What specific treatment, if any, was used

Instructions will be given to sites to additionally report episodes consistent with hypoglycemia requiring third party assistance as Serious Adverse Events (SAE).

Collection of data from the hypoglycemia AE eCRF including episodes consistent with hypoglycemia as well as review of SMBG values with or without symptoms will allow analysis and characterization of hypoglycemia according to accepted ADA definitions (Seaquist et al, 2013) and according to common cut-off values, such as BG < 70 mg/dL and < 53 mg/dL for example.

7.3.2 Adverse Events of Hyperglycemia

Hyperglycemia is the result of inadequate treatment and a pre-condition for enrolment into the study, therefore in general hyperglycemia is not considered an AE. However, hyperglycemia may occur in participants during the study either due to worsening diabetes or lack of efficacy of study medication. For standardization purposes, hyperglycemia is defined as a blood glucose reading >300 mg/dL regardless of symptoms. Subjects who have a blood glucose reading >300 mg/dL will have the reading repeated 1-2 hours later. If a subject's glucose remains above 300 mg/dL or for persistent symptoms of hyperglycemia, the subject will be instructed to contact the investigative site for follow-up. Protocol specified algorithms will allow subjects to receive additional rescue medication that may enable them to remain in the study (Section 3.7).

7.4 Definition of Serious Adverse Event

A SAE is defined in 21 CFR 312.32(a) as follows:

An AE is considered "serious" if, in the view of either the investigator or Sponsor, it results in any of the following outcomes:

- Death;
- Life-threatening AE;
- Inpatient hospitalization or prolongation of existing hospitalization;
- Persistent or significant incapacity or substantial disruption of the ability to conduct normal life functions;
- Congenital anomaly/birth defect.

Important medical events that may not result in death, be life-threatening, or require hospitalization may be considered serious when, based upon appropriate medical judgment, they may jeopardize the subject or subject and may require medical or surgical intervention to prevent one of the outcomes listed in this definition. Examples of such medical events include allergic bronchospasm requiring intensive treatment in an emergency room or at home, blood dyscrasias or convulsions that do not result in inpatient hospitalization, or the development of drug dependency or drug abuse.

An AE is considered "life-threatening" if, in the view of either the investigator or Sponsor, its occurrence places the subject or subject at immediate risk of death. It does not include an AE that, had it occurred in a more severe form, might have caused death.

7.5 Eliciting and Reporting of Adverse Events

AE monitoring will start immediately following the first dose of run-in placebo and will continue through the Follow-Up Visit. Any subject with a possible study treatment-related AE at the Follow-Up Visit will be followed until resolution or stabilization of the event. Further, any SAE, whether or not related to study treatment that occurs within 30 days following the last dose of study

treatment will be followed until resolution or stabilization of the event. This may require additional clinical assessments and laboratory tests. The follow-up results will be recorded in the subject's source documentation and in the eCRF.

Subjects will be instructed to report all AEs experienced during the study, and subjects will be assessed in clinic for the occurrence of AEs throughout the study. In order to avoid bias in eliciting AEs, subjects will be asked general, non-leading questions such as "How are you feeling?"

All AEs, including pretreatment and TEAEs, reported by the subject, observed or otherwise identified by the Investigator, or other Investigational Site personnel will be documented. Medical conditions existing at Screening should be recorded as medical history. New or worsening pre-existing medical conditions or diseases are considered AEs if they arise or worsen after the Screening visit, and should be recorded as AEs.

Surgical procedures themselves are not AEs; they are therapeutic measures for conditions that require surgery. The condition for which the surgery is required is an AE if it occurs or is detected following the first dose of Study treatment through the Follow-Up Visit. Conditions leading to planned surgical procedures are not AEs if the condition(s) was (were) known before study treatment. In the latter case, the condition should be reported as medical history.

7.5.1 Routine Reporting of Adverse Events

All AEs, whether or not associated with the study treatment, that are observed by the Investigator, other Investigational Site personnel, or those reported by the subject will be recorded in the subject's source documentation and on the AE page of the eCRF. Copies of the SAE CRF pages or an SAE listing generated based on the eCRF pages will be submitted to the Sponsor at regularly scheduled intervals to allow the Sponsor to meet expedited regulatory reporting requirements under 21 CFR 312.32 (see Section 7.5.2 for further detail) and regular regulatory reporting requirements under 21 CFR 312.33.

For each AE, the following information will be entered in the eCRF:

- Medical diagnosis of the event in standard medical terminology (if a medical diagnosis cannot be determined, a description of each sign or symptom characterizing the event);
- Date of onset of any new AE or worsening of a previously observed AE.
- Date of resolution of the event (or confirmation ongoing).;
- Whether the event is serious (per definition in Section 7.3), and if so, the reason it is considered serious;
- Severity of AE (per definition in Section 7.7);
- Assessment of the attributability of the AE to the study treatment [per definition in Section 7.5];
- Whether the event is expected (per definition in Section 7.8);
- Action taken in treating the AE (including concomitant medications or therapies administered) and/or change in the study treatment administration or dose (including whether the study treatment was temporarily interrupted or discontinued);
- Outcome of AE (per definition in Section 7.9).

7.5.2 Reporting of Serious Adverse Events, Including Death

The Sponsor will adhere to all expedited regulatory reporting requirements as per 21 CFR 312.32.

SAEs, including death due to any cause, which occur during this study or within 30 days following the last dose of the study treatment, whether or not related to the administration of study treatment, must be reported by the Investigator or other Investigational Site personnel to the Medical Monitor by telephone or fax within 24 hours of learning of the event. The contact information for the Medical Monitor is provided below.

Medical Monitor:

[name] Safety Office, Integrium, LLC

Office: [contact] Cellular: [contact]

Email: [contact]

SAE Forms will be provided by the Sponsor or Sponsor designated contract research organization (CRO). If all information is not known at the time of initial reporting, an initial report should still be made. In the event there is a question as to whether the experience is serious, the information should be forwarded to the Medical Monitor for review. The Investigator is responsible for following up on completion of the SAE Form. The Investigator will submit substantiating data in hard copy form, such as diagnostic test reports and progress notes, to the Medical Monitor. In the case of fatality, autopsy reports will be furnished to the Medical Monitor as soon as available. If the Medical Monitor is informed of a SAE via a telephone call, preliminary information will be obtained, and the study site will be instructed to fax an SAE Form.

In the event of a medical emergency or an SAE that is unexpected (as defined in Section 7.8) and possibly related to the study treatment (s) (i.e., an adverse reaction or suspected adverse reaction as defined in Section 7.6), in the opinion of either the Investigator or the Medical Monitor, the blind will be broken for the subject that experiences the event. An emergency code break envelope for each subject will be provided to the Investigational Site and also to the Medical Monitor. If the Investigational Site personnel need to unblind the study treatment and cannot access the relevant code break envelope at the site, they can contact the Medical Monitor.

The initial SAE Form and any subsequent follow-up SAE Forms submitted to provide more accurate, corrected, or new information must be signed by the Investigator. The Investigator and Investigational Site Personnel must make every reasonable effort to obtain, from other institutions if necessary, all supporting medical case records as needed to comply with expedited Investigational New Drug application (IND) safety reporting requirements.

If the SAE involves expedited IND safety reporting (as determined by the Sponsor or designee), all supporting medical records must be submitted to the Sponsor or designee within 4 calendar days for death or life-threatening events, and 10 calendar days for all other events. In cases where medical records and supporting documentation are unobtainable, the Investigator must generate a narrative

of the event utilizing, when necessary, interviews with the subject, their family members and care givers as appropriate.

The Investigator must also promptly inform the governing IRB of the SAE in accordance with the governing IRB's requirements. Any SAE that is determined by the Sponsor to be reportable to the FDA as an IND Safety Report (as defined in 21 CFR 312.32) will be reported to FDA by the Sponsor or designee within the specified time frame. All IND Safety Reports will also be promptly provided to the Investigator for submission to his/her IRB. Similarly, any SAE that is determined by the Sponsor to require expedited reporting to other regulatory authorities will be reported to the appropriate authorities by the Sponsor or designee within the specified time frames, and will be provided to the Investigator for submission to his/her IRB.

The Investigator, Medical Monitor, and Sponsor will review each SAE report and evaluate the relationship of the adverse experience to study treatment and to underlying disease. Based on this assessment, a decision will be made concerning the need for further action. The primary consideration governing further action is whether new findings affect the safety of subjects participating in the clinical trial. If the discovery of a new adverse experience related to the study treatment raises concern over the safety of continued administration of study treatment, the Sponsor will take immediate steps to notify the regulatory authorities.

Further action that may be required includes the following:

- 1. Alteration of existing research by modification of the protocol;
- 2. Discontinuation or suspension of the study;
- 3. Alteration of the informed consent process by modification of the existing consent form and informing current study participants of new findings;
- 4. Modification of previously identified expected adverse experiences to include adverse experiences newly identified as study treatment-related.

If the subject or partner of a subject participating in the study becomes pregnant during the study or within 30 days of discontinuing study medication, the Investigator should report the pregnancy to Integrium within 24 hours of being notified. Safety personnel will then forward the Exposure In Utero form to the Investigator for completion.

The subject or partner should be followed by the Investigator until completion of the pregnancy. If the pregnancy ends for any reason before the anticipated date, the Investigator should notify the Sponsor. At the completion of the pregnancy, the Investigator will document the outcome of the pregnancy. If the outcome of the pregnancy meets the criteria for immediate classification as an SAE (i.e., postpartum complication, spontaneous abortion, stillbirth, neonatal death, or congenital anomaly), the Investigator should follow the procedures for reporting an SAE.

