3.6 Follow-Up

3.6.1 Visit 10 (Part 2 Week 12 ± 7 days)

Subjects will report to the clinic in the morning following a 10-hour fast and the following procedures will be performed:

- Review of prior and current medications and supplements.
- Physical examination.
- Measurement of weight.
- Measurement of vital signs (SBP/DPB and heart rate).
- Collection of fasted blood and urine samples for:
 - o Clinical safety labs, including hematology, serum chemistry (with FPG and A1C), and urinalysis (see Section 6.1.5 for list of tests).
 - o Urine pregnancy test (WCBP only).
- Discharge from the study.

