3.8 Early Withdrawal (EW)

If a randomized subject is withdrawn from the study prior to completion, the subject will be instructed to return to the clinic the next day and the Visit 9 procedures will be performed. In addition, subjects will perform the DTSQs and DTSQc questionnaires. Subjects will then be discharged from the study.

Any subject with a possible study treatment related AE at the time of EW will be followed until resolution or stabilization of the event.

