If either of the criteria listed below is met, enrollment of new subjects and dosing of ongoing subjects will be temporarily stopped. The Investigator, Sponsor, and the Medical Monitor will discuss whether a lower dose or any additional treatment guidelines should be implemented, or if the trial should be permanently stopped. Any proposed changes to the protocol to address such findings will be submitted for review and approval by the IRB and FDA prior to re-starting the trial.

- 1. A death within 30 days after study treatment administration where there is a reasonable possibility that the drug caused the event;
- 2. Two Grade 4 AEs where there is a reasonable possibility that the study treatment caused the events.

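### Deaths, SAEs and pregnancies are reportable for 30 days after treatment, but scheduled contact ends about two weeks after the last dose, or the day after an early withdrawal

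*Combined protocol and SAP*

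**What the plan says.** **The 30-day rules.**

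- Section 7.5.2 makes SAEs, including deaths from any cause, reportable if they are events "which occur during this study or within 30 days following the last dose of the study treatment", related or not. The site must report them "within 24 hours of learning of the event".
- Section 7.5 adds that "any SAE, whether or not related to study treatment that occurs within 30 days following the last dose of study" treatment is followed until it resolves or stabilises.
- Section 7.5.2 also makes a pregnancy in a subject or partner reportable for 30 days after study medication is discontinued.
- Section 4.3 stops enrolment and dosing temporarily if either of two criteria is met. The first is "A death within 30 days after study treatment administration where there is a reasonable possibility that the drug caused the event". The second is two possibly related Grade 4 AEs, with no day window.

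**The contact schedule.**

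- Section 7.5: "AE monitoring will start immediately following the first dose of run-in placebo and will continue through the Follow-Up Visit".
- Section 3.6.1 places that visit, Visit 10, at Part 2 Week 12 and ends it with discharge. The Synopsis puts it two weeks after the end of Part 2.
- Section 3.8 brings early withdrawals back the next day for the Visit 9 procedures and the satisfaction questionnaires, and then: "Subjects will then be discharged from the study".
- Table 1 has no column after Visit 10, and no section describes a later call or vital-status check.

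**The concern.** The sponsor has chosen 30 days as the period over which deaths, SAEs and pregnancies matter, and has tied one trial-level pause criterion to it. The schedule contains no step that would find out whether such an event happened in the later part of that period. The 24-hour reporting clock starts only when the site learns of the event, and nothing prompts the site to ask.

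One qualifying death is enough to trigger the pause while other subjects may still be dosing, so one undetected death after discharge would leave that criterion unapplied. An SAE or pregnancy after discharge could be missed in the same way. The uncovered period is longest for subjects who leave early, because they have no Visit 10.

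**Working it through.** **Inputs**

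- Visit 9: Part 2 Week 10 ± 7 days (Section 3.5.4), nominal day 10 × 7 = 70.
- Visit 10: Part 2 Week 12 ± 7 days (Section 3.6.1), nominal day 12 × 7 = 84.
- Dosing runs to Visit 9 (Section 5.3.1.2). Section 3.5.4 gives a dose at Visit 9 itself in the BID and TID arms.
- Assumption: a QHS subject takes the last dose on the evening before Visit 9.
- Early-withdrawal visit: the day after withdrawal (Section 3.8).
- Reporting window: 30 days (Section 7.5.2).
- Planned completers: 192 of 240 in Cohort A (Section 8.2.1) and 60 of 75 in Cohort B (Section 8.2.2).

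**Step 1. Reproduce the stated interval.** Visit 10 − Visit 9 = 84 − 70 = 14 days. This matches the two weeks in the Synopsis.

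**Step 2. Completers, nominal schedule.** Uncovered days = 30 − (days from last dose to Visit 10).

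- BID/TID: 30 − 14 = 16 days.
- QHS: 30 − (14 + 1) = 15 days.

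**Step 3. Completers, with both visit windows.**

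- Shortest interval between visits: (84 − 7) − (70 + 7) = 0 days.
- Longest interval between visits: (84 + 7) − (70 − 7) = 28 days.

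| Regimen | Last dose to Visit 10, nominal (range) | Uncovered of 30 days, nominal (range) |
|---|---|---|
| BID/TID | 14 (0 to 28) | 16 (2 to 30) |
| QHS | 15 (1 to 29) | 15 (1 to 29) |

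No permitted schedule reaches day 30.

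**Step 4. Early withdrawals.**

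- Last dose on the day of withdrawal: 30 − 1 = 29 days uncovered.
- A dose given at the early-withdrawal visit as part of the Visit 9 meal test: 30 − 0 = 30 days.
- Dosing stopped *d* days before withdrawal: 29 − *d* days.

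**Step 5. How many subjects could have the longer gap.**

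- Cohort A: 240 − 192 = 48.
- Cohort B: 75 − 60 = 15.
- Total: 48 + 15 = 63 of 315, which is 20%.

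These are counts of days and people without scheduled contact. The documents give no event rate for the period after discharge, so the number of missed events cannot be estimated.

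**The case against.** The strongest reply is that nothing here is contradictory. Section 7.5 sets active elicitation through Visit 10; Section 7.5.2 sets a longer period during which anything the site hears must be reported. Active follow-up followed by a passive notification period is a coherent scheme. That stands, and the point is therefore an improvement and not the repair of an error.

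The second reply is that safeguards exist.

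- Possibly related AEs present at early withdrawal (Section 3.8) or at the Follow-Up Visit (Sections 7.5 and 7.9) are followed to resolution or stabilisation.
- Significant clinical findings at the Follow-Up Visit are also followed (Section 7.10).
- Section 4.3 asks for every effort to reach subjects who miss follow-up appointments or contacts.

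These do narrow the gap. The first two cover what is already present at discharge, however, and the third applies to missed contacts, of which a discharged subject has none scheduled. None of them finds a new event after discharge. Consent pages were not available, so what subjects are told about reporting after discharge cannot be judged.

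A reader might also infer more than the documents support:

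- *That SAEs in general trigger the pause.* They do not. Only a possibly drug-caused death carries the 30-day window; the other criterion is two possibly related Grade 4 AEs, with no window.
- *That the 30-day rule is unworkable throughout.* Subjects attend Visits 3 to 9 during treatment. Only the period after discharge is passive.
- *That early stoppers are the subjects most likely to have late events.* Nothing in the documents shows this.
- *That SAE rates will not be comparable.* Section 8.6.2 plans descriptive tables by treatment group and no inferential comparison of active with placebo, and the documents give no reason to expect withdrawal to differ by arm.

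**Conclusion.** The concern holds as a gap in finding events. New deaths, SAEs and pregnancies between discharge and day 30 reach the sponsor only passively. The gap is nominally 15 to 16 of 30 days for completers and about 29 of 30 for early withdrawals.

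The first figure assumes on-time visits and a last dose at Visit 9 or the evening before. The second assumes that dosing stopped on the day of withdrawal and that the subject attended the next day.

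The count of 63 uses the protocol's approximate 20% as it is applied there, to 240 and 75. A reader might instead take 20% of the 340 subjects to be randomised (265 + 75) and arrive at 68, but the sample-size section does not apply its allowance to 265. The 20% is in any case a planning allowance for non-completion. Some of those subjects may never attend a withdrawal visit, so 63 is the number who could have the longer gap, not a forecast.

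The change is worth making because it is cheap and brings contact into line with a window that the sponsor set.

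**What to change.** Add to Sections 3.6, 3.8 and 7.5, and to Table 1, one scripted telephone contact at or just after day 30 from the last dose. It should cover every dosed subject, including the 20 non-randomised subjects on excipient-matched placebo and early withdrawals who have not refused further contact. The script asks about death (through a contact person where needed), hospitalisation, any other SAE, and pregnancy in the subject or partner.

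Nominally the call falls 15 to 16 days after Visit 10, or about 29 days after an early-withdrawal visit when dosing stopped at withdrawal. It changes no treatment, endpoint or sample size.

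The cost is one short call per subject by existing site staff, a protocol amendment, and possibly a matching edit to the consent form if that now ends contact at discharge. Subjects who refuse contact or cannot be reached will remain uncovered, so the outcome of each call attempt should be recorded.
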